3.3.1 Inclusion Criteria

Patients are eligible for this trial if all of the following inclusion criteria are met:

1. Has histologically or cytologically confirmed CRC with liver metastases. In addition to liver metastases, extrahepatic metastases (e.g. pulmonary metastases) may be permitted if all

other eligibility criteria are met. Patients are permitted to have primary tumor *in situ* (Neoadjuvant Arm only).

2. Has received previous oxaliplatin-based chemotherapy.
 - a. FOLFOX or CapeOx does not need to be a direct lead-in to this study.
 - b. If chemotherapy is a direct lead-in to this study, concurrent mAb therapy (bevacizumab, cetuximab, or panitumumab) is acceptable, however the antibody must be omitted from the final cycle of chemotherapy prior to pembrolizumab.
3. Is an appropriate candidate to undergo liver biopsy and resection (\pm ablation) of liver metastases (Neoadjuvant Arm Only)
4. Is willing and able to provide written informed consent/assent for the trial. The patient may also provide consent for Future Biomedical Research. However, the patient may participate in the main trial without participating in Future Biomedical Research.
5. Is ≥ 18 years of age on day of signing informed consent.
6. Has measurable disease based on RECIST 1.1 as assessed by the investigator. Lesions situated in a previously irradiated area are considered measurable if progression has been demonstrated in such lesions. (Neoadjuvant Arm Only)
7. Is willing to provide tissue from a newly obtained core or excisional biopsy of a tumor lesion. Newly-obtained is defined as a specimen obtained after last dose of standard of care lead-in chemotherapy [if applicable] and within 28 days prior to first dose of pembrolizumab. (Neoadjuvant Arm Only)
8. Has a performance status of 0 or 1 on the Eastern Cooperative Oncology Group (ECOG) Performance Scale (Appendix 1).
9. Has adequate organ function as defined in Table 1, within 10 days of treatment initiation.

Table 1 Adequate Organ Function Laboratory Values

System	Laboratory Value
Hematological	
Absolute neutrophil count (ANC)	$\geq 1,500/\mu\text{L}$
Platelets	$\geq 100,000/\mu\text{L}$
Hemoglobin	$\geq 9 \text{ g/dL}$ or $\geq 5.6 \text{ mmol/L}$ without transfusion or erythropoietin (EPO) dependency (within 7 days of assessment)
Renal	

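### The albumin row of Table 1 is printed in mg/dL, 1,000-fold below the g/dL scale, so taken literally that one row excludes no one; probably a unit slip, minor and easily corrected.

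*Combined protocol and SAP*

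**What the plan says.** Section 3.3.1 makes every inclusion criterion mandatory: "Patients are eligible for this trial if all of the following inclusion criteria are met". Criterion 9 is one of them: "Has adequate organ function as defined in Table 1, within 10 days of treatment initiation".

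The hepatic block of Table 1 has three rows:

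- total bilirubin, with a direct-bilirubin alternative;
- AST and ALT, at no more than 2.5 times the upper limit of normal;
- albumin, at > 2.5 mg/dL.

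Hemoglobin, in the hematological block of the same table, is given in g/dL with a mmol/L equivalent.

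Albumin is named in two other places: the screening chemistry list in Section 6.1.1 and the chemistry column of Table 12 in Section 6.9.1. Neither gives a unit or a limit, so the Table 1 row is the only albumin threshold in the document.

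The same row also governs the second treatment phase. The outline of optional adjuvant treatment in the abstract and footnote a of Table 11 both refer back to Section 3.3. Several criteria in Section 3.3 are marked as applying to the neoadjuvant arm only; criterion 9 is not.

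**The concern.** A threshold works only if some patients could fall on the wrong side of it. The number 2.5 is plausible for albumin in g/dL. In mg/dL it lies far below any value a living patient would have, so the number and the unit cannot both be what the authors meant.

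The row is an operative eligibility limit and not background text. It is one of three hepatic limits in a trial whose patients are about to have part of the liver removed, and it applies again when they are considered for adjuvant treatment. What is at stake is whether the written eligibility rule contains the albumin screen that its authors evidently intended. No derived statistical quantity depends on it.

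**Working it through.** There is no computed figure to reproduce here. The check is a unit conversion, followed by applying the limit as printed and in g/dL to a range of albumin values.

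**Inputs**

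- Limit as printed: > 2.5 mg/dL (Table 1, albumin row).
- Conversion: 1 g/dL = 1,000 mg/dL.
- Scale and range of serum albumin: measured in g/dL, 1.0 to 5.5 g/dL. This is an assumption from general laboratory knowledge and is not stated in the documents.

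**Step 1: the printed limit on the g/dL scale**

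2.5 mg/dL ÷ 1,000 = 0.0025 g/dL. This is exactly 1,000-fold below 2.5 g/dL.

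**Step 2: both limits applied**

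Ratio to printed limit = (albumin in g/dL × 1,000) ÷ 2.5.

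| Albumin (g/dL) | Albumin (mg/dL) | Ratio to printed limit | > 2.5 mg/dL (as printed) | > 2.5 g/dL |
|---|---|---|---|---|
| 1.0 | 1,000 | 400 | pass | fail |
| 1.5 | 1,500 | 600 | pass | fail |
| 2.0 | 2,000 | 800 | pass | fail |
| 2.5 | 2,500 | 1,000 | pass | fail |
| 3.5 | 3,500 | 1,400 | pass | pass |
| 5.0 | 5,000 | 2,000 | pass | pass |
| 5.5 | 5,500 | 2,200 | pass | pass |

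As printed, all seven values pass. In g/dL, the four values from 1.0 to 2.5 fail (2.5 itself fails because the inequality is strict) and the three higher values pass, so the row can exclude a patient.

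**Step 3: sensitivity to the assumed range**

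The result does not depend on where the range ends. To fail the printed limit, a patient's albumin would have to be 0.0025 g/dL or less, which is 400 times below the lowest value considered.

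**Step 4: could another section supply the missing unit?**

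Section 6.1.1 and Table 12 list albumin as a test only. Nothing else in the document gives a limit or a unit that would override the row.

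**Step 5: could this be a text-extraction fault?**

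The number and the unit in the cell are both legible, nothing there is redacted, and the g/dL unit for hemoglobin in the same table came through correctly. An extraction fault is therefore unlikely, and a glance at the source PDF would settle it.

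**The case against.** The strongest reply is that this is an obvious typing slip that would mislead nobody. No clinician would take a limit of 0.0025 g/dL as intended, 2.5 is a natural number on the g/dL scale, and hemoglobin in the same table is in g/dL. The trial runs at a single site (Section 8.1.1), so different sites cannot read the row in different ways. This stands, and it is why the practical effect is likely small. It does not make the printed row correct.

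A reader might go further and infer that nothing screens hepatic function before resection. The documents do not support that. The following remain in force:

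- the bilirubin, AST/ALT, INR/PT and aPTT rows of Table 1;
- for the neoadjuvant arm, criterion 3: "Is an appropriate candidate to undergo liver biopsy and resection";
- exclusion 14, which covers laboratory abnormalities that make participation contrary to the patient's interest;
- exclusions 20 and 22, on encephalopathy and on symptomatic ascites or pleural effusion;
- Section 6.9.1, under which screening laboratory results must be reviewed and judged acceptable before dosing;
- the repeat serum chemistry before surgery in Section 6.1.3, with the operative plan left to the surgeon.

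A patient with an albumin of 1.5 g/dL would pass the albumin row as printed but would still face these checks.

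A reader might also link the row to the early stopping rule, reasoning that a patient with poor hepatic reserve could be enrolled, suffer a Grade IV or V surgical complication and help to stop the trial. That does not follow either. The notes in Sections 5.1.4 and 8.3 say that such complications need not stop the study and will be discussed first. The opening paragraph of Section 8.3 also requires attribution to the study treatment, so a complication due to low albumin would not clearly count.

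Finally, a reader might suppose that an audit under Section 9.7 would pass an unsuitable patient on the literal wording. Nothing in the documents indicates that an auditor would apply a limit no patient could fail.

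**Conclusion.** The albumin row is wrong as written, and the severity is minor. The printed limit is 1,000-fold below the g/dL scale. Across an assumed 1.0 to 5.5 g/dL it is cleared by a factor of 400 to 2,200, so taken literally this row excludes no one.

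The conclusion covers that row alone. The other hepatic, coagulation and surgical-candidacy requirements still work. How many patients a limit of > 2.5 g/dL would exclude cannot be estimated, because the documents give no albumin distribution for this population. With a likely reading of g/dL at the one site, the effect on who is enrolled is probably small. Sample size, power and alpha are not affected.

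The verdict rests on one assumption from outside the documents, that serum albumin is measured in g/dL and lies within roughly the stated range. The factor of 1,000 itself is exact.

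**What to change.** In Table 1 of Section 3.3.1, change the unit in the albumin row from mg/dL to g/dL, so that it reads > 2.5 g/dL. The sponsor should confirm that 2.5 is the intended clinical cut-off and that g/dL is the unit the site laboratory reports. Make the same change in the eligibility checklist, and apply it to adjuvant as well as neoadjuvant entry, since both rely on Section 3.3.

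The cost is one table cell and one checklist entry, which can go into the next amendment. No analysis, sample-size statement or visit schedule needs to change.

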3.3.2 Exclusion Criteria

The patient must be excluded from participating in the trial if the patient:

1. Is currently participating and receiving study therapy or has participated in a study of an investigational agent and received study therapy or used an investigational device within 4 weeks of the first dose of treatment.

Note: Patients who have entered the follow-up phase of an investigational study may participate as long as it has been 4 weeks since the last dose of the previous investigational agent or device use.

2. Has a diagnosis of immunodeficiency or is receiving chronic systemic steroid therapy (in dosing exceeding 10 mg daily of prednisone equivalent) or any other form of immunosuppressive therapy within 7 days prior to the first dose of trial treatment.
3. Has a known history of human immunodeficiency virus (HIV) infection. No HIV testing is required unless mandated by local health authority.

Phase 2, Pembrolizumab, Vactosertib

4. Has an active autoimmune disease that has required systemic treatment in past 2 years (i.e., with use of disease-modifying agents, corticosteroids, or immunosuppressive drugs). Replacement therapy (e.g., thyroxine, insulin, or physiologic corticosteroid replacement therapy for adrenal or pituitary insufficiency) is not considered a form of systemic treatment and is allowed.
5. Has active Hepatitis B (defined as Hepatitis B surface antigen [HBsAg] reactive) or active Hepatitis C virus (defined as HCV RNA [qualitative] [32] is detected) infection.
6. Has received prior anti-cancer mAb, systemic anticancer therapy other than FOLFOX (including investigational agents), targeted small molecule therapy, or radiation therapy within 14 days prior to the first dose of study treatment (Day 1). Note: patients must have recovered from all AEs due to a previous therapies to ≤Grade 1 or baseline. Patients with Grade 2 neuropathy or alopecia are eligible. If a patient received major surgery, they must have recovered adequately from the toxicity and/or complications from the intervention prior to starting study treatment.
7. Has received FOLFOX less than 7 days prior to the first dose of study treatment (Day 1). Has not recovered (i.e., ≤Grade 1 or at baseline) from AEs due to FOLFOX chemotherapy. Note: Patients with ≤Grade 2 neuropathy or alopecia are exceptions to this criterion and may qualify for the study.
8. Has not recovered adequately from toxicity or complications of a surgery or other procedure, per the assessment of the treating investigator.
9. Has received liver-directed therapy such as radiotherapy or yttrium-90 in the past year involving the lesion to be biopsied. (Neoadjuvant Arm only)
10. Has a known additional malignancy that is progressing or has required active treatment within 5 years prior. Note: Patients with basal cell carcinoma of the skin, squamous cell carcinoma of the skin, carcinoma in situ (e.g. breast carcinoma, cervical cancer in situ) that have undergone potentially curative therapy are not excluded.
11. Has known active central nervous system (CNS) metastases and/or carcinomatous meningitis. Patients with previously treated brain metastases may participate provided they are radiologically stable (i.e., without evidence of progression by imaging for at least 4 weeks by repeat imaging [repeat imaging should be performed during the study screening]), clinically stable, and without requirement of steroid treatment for at least 14 days prior to trial treatment. This exception does not include carcinomatous meningitis which is excluded regardless of clinical stability.
12. Has a history of (noninfectious) pneumonitis that required steroids or has current pneumonitis.
13. Has an active infection requiring systemic therapy.
14. Has a history or current evidence of any condition, therapy, or laboratory abnormality that might confound the results of the trial, interfere with the patient's participation for the full duration of the trial, or is not in the best interest of the patient to participate, in the opinion

of the treating investigator. Anticoagulation that cannot be safely held to perform the liver biopsy is an example of a contraindication to participation.

15. Has known psychiatric or substance abuse disorders that would interfere with cooperation with the requirements of the trial.
16. Has received any prior immunotherapy including anti-PD-1, anti-PD-L1, or anti-PD-L2 or with an agent directed to another stimulatory or co-inhibitory T-cell receptor (e.g. CTLA-4, OX-40, CD137) (Neoadjuvant Arm Only).
17. Has severe hypersensitivity (\geq Grade 3) to pembrolizumab or vactosertib and/or to any of their excipients.
18. Has received a live or live-attenuated vaccine within 30 days prior to first dose of the trial drug. Administration of killed vaccines are allowed.
19. Has inferior vena cava/cardiac involvement based on imaging.
20. Has had encephalopathy in the last 6 months. Those patients on rifaximin or lactulose to control their encephalopathy are not allowed.
21. Has had a solid organ or hematologic transplant.
22. Has symptomatic ascites or pleural effusion. A patient who is clinically stable following treatment for these conditions (including therapeutic thora- or paracentesis) is eligible.
23. Uncontrolled intercurrent illness, including but not limited to, ongoing or active infection, symptomatic congestive heart failure (New York Heart Association Class III/IV), uncontrolled hypertension (\geq 150/90mmHg), unstable angina pectoris or myocardial infarction (\leq 6 months prior to screening), uncontrolled cardiac arrhythmia, clinically significant cardiac valvulopathy requiring treatment, active interstitial lung disease, or serious chronic gastrointestinal conditions associated with diarrhea.

3.4 Duration of Therapy

All participants will receive a single dose of pembrolizumab and 20 doses of vactosertib (QD, 5 days per week for 2 weeks) prior to surgery.

Participants who undergo surgical resection and have adequately recovered from toxicity or complications of a surgery or other procedure, per the assessment of the treating investigator, may receive optional adjuvant treatment of pembrolizumab + vactosertib for up to eight 6-week cycles.

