Study Drugs	
Neoadjuvant pembrolizumab will be administered at a fixed dose of 200 mg (IV) for 1 cycle plus 200 mg vactosertib (PO QD, 5 days per week x 2 weeks).
 
Adjuvant pembrolizumab (400 mg IV) + vactosertib (200 mg PO QD Cycle 1, 5 days per week, Cycles 2 and beyond 200 mg BID, 5 days per week) will be administered for up to eight 6-week cycles.

Phase 2, Pembrolizumab, Vactosertib

Safety Assessments	Safety assessments will include adverse events, clinical laboratory evaluations, and vital signs.
Efficacy Assessments	Objective response rate, pathologic response rate, R0 resection rate, and 1-year and 2-year RFS.
Unique Aspects of this Study	This is the first study to evaluate the safety and efficacy of pembrolizumab plus vactosertib following FOLFOX chemotherapy in patients with metastatic CRC undergoing liver resection with curative intent. Biopsy of a liver metastasis prior to administering pembrolizumab plus vactosertib and resection of the liver metastases following 1 cycle of pembrolizumab plus vactosertib will enable extensive scientific correlatives.

Study Schema

The above timeline is approximate with further guidelines below:

- A screening computed tomography (CT) chest/abdomen/pelvis with intravenous (IV) contrast must be performed and reviewed to confirm candidacy for hepatic resection prior to study entry.
- If chemotherapy is a direct lead-in to study enrollment, then liver resection surgery should be performed within 4-6 weeks of the final chemotherapy administration. During this 4-6 week window, 1 cycle of pembrolizumab plus vactosertib will be administered approximately 2 weeks (minimum 1 week) after the last dose of chemotherapy, and surgery will occur approximately 2 weeks (minimum 1 week) after C1D1.
- Labs, including liver function testing will be performed after C1D1, as close to surgery as possible.

Phase 2, Pembrolizumab, Vactosertib

- In the event that the surgery is canceled, and the first liver biopsy yielded adequate tumor material, a second liver biopsy will be requested (same lesion as the first biopsy preferred).
- Participants will be followed for up to 2 years after surgery or will be offered optional adjuvant treatment (described below).

Optional Adjuvant Treatment

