1.3.2 Rationale for Dose Regimen

The planned dose of pembrolizumab for this study is 200 mg (IV) for 1 neoadjuvant cycle and 400 mg (IV) for up to eight 6-week adjuvant cycles (optional). The pembrolizumab doses used in this trial have been demonstrated to be well tolerated in earlier clinical trials.

The planned dose of vactosertib for this study is 200 mg PO QD, 5 days per week for 2 weeks during the neoadjuvant treatment period, and 200 mg PO QD, 5 days per week for 6 weeks (1 cycle) and depending on tolerability, patients will receive 200 mg PO BID, 5 days per week for up to 42 weeks (7 cycles) during the optional adjuvant treatment period. The vactosertib dosing regimen used in this trial has been demonstrated to be well tolerated in the ongoing early phase clinical trials.

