5.1 Dosage and Administration

Trial treatment should be administered at the time points specified in the Trial Flow Charts (section 6.2). The treatment to be used in this trial is outlined in Table 4 and Table 5. On Day 1 of each cycle, administer vactosertib after the subject completes their pembrolizumab infusion. Vactosertib may be administered as soon as the pembrolizumab infusion is completed. Vactosertib and pembrolizumab may be administered without regard to meals.

Table 4 Main Trial Treatment

Drug	Dose/ Potency	Dose Frequency	Route of Administration	Regimen/ Treatment Period	Use
Pembrolizumab	200 mg	Once	IV infusion	C1D1	Experimental
Vactosertib	200 mg	QD, 5 days per week	PO	C1D1 through C1D14	Experimental

Abbreviation: IV = intravenous, PO = per os, C = cycle, D = day, QD = once a day

Table 5 Optional Adjuvant Treatment Cohort

Drug	Dose/ Potency	Dose Frequency	Route of Administration	Regimen/ Treatment Period	Use
Pembrolizumab	400 mg	Q6W	IV infusion	Up to 8 cycles	Experimental
Vactosertib	200 mg	Cycle 1: QD, 5 days per week Cycles 2+: BID, 5 days per week	PO	Up to 8 cycles	Experimental

Abbreviation: IV = intravenous, PO = per os, C = cycle, D = day, Q6W = every 6 weeks, QD = once a day, BID = twice a day

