5.1.2 Vactosertib

Vactosertib will be administered once daily at 200 mg PO for 5 days followed by a 2-day resting period (5 days on/2 days off) for two weeks during the neoadjuvant treatment phase.

During the optional adjuvant treatment phase, vactosertib will be administered once daily at 200 mg PO (dose level -1) for 5 days followed by a 2-day resting period during Cycle 1. If no significant drug-related toxicities are observed, vactosertib will be administered twice daily at 200 mg PO (dose level 0) for 5 days followed by a 2-day resting period (5 days on/2 days off) for up to 8 cycles.

Please see Section 5.2, Dose Modifications and Dosing Delays for additional details.

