- Obtain standard of care MSI/MMR and expanded RAS/BRAF mutation testing from liver resection specimen if not tested previously. Review pathology report.
- Baseline medications taken within 28 days of C1D1.
- Repeat liver biopsy if patient unable to undergo liver resection surgery.

- f. Stool collection at following time points ± 2 day window: mandatory collection post-chemo/ pre-C1D1 on day minus 4 and day minus 2, mandatory collection post-C1D1/ pre-surgery; optional at post-surgical follow-up.
- g. Review of baseline imaging to establish anticipated candidacy for liver resection.
- h. Baseline imaging should include a CT chest and IV contrast-enhanced CT or magnetic resonance imaging (MRI) abdomen/pelvis.
- i. Can be performed within 7 days prior to C1D1.
- j. Pembrolizumab will be administered at a fixed dose of 200 mg (IV) and vactosertib will be taken QD, PO 5 days per week C1D1 through C1D14 . See section 5.1.
- k. All participants will be followed for up to 1 year after the last dose of pembrolizumab is administered or up to 2 years after surgery whichever occurs last.
- l. Interested participants will complete the pre-treatment procedures outlined in Table 11 below and section 6.1.6.1.
- m. Participants who are not interested or are ineligible for the adjuvant treatment cohort will be followed Q90D ± 14 d post-surgery for up to 2 years as outlined in Table 10 and section 6.1.7.
- n. Can be performed within 10 days of C1D1
- o. Not needed for eligibility. Every effort should be made to collect archival tissue samples but if sample is not collected or unavailable it should not constitute a protocol deviation.
- p. For tumor marker assessments (CEA): record CEA at diagnosis, prior to and after lead-in FOLFOX/CapeOx

Table 11 Flow Chart for Adjuvant Treatment Cohort

Trial Period:	Pre-Treatment	Adjuvant Treatment				Post-Treatment		
		C1 D1	C2 D1	C3 D1	C4-8 D1	End of TX	Safety F/U	Follow Up Phase ^g
Scheduling Window:	2w ±14d post-op	6w ±14d post-op	12w ±3d post-op	18w ±3d post-op	24w-48w ±3d post-op	At DC +7d	30d after DC +7d	D90D ±14d post-last pembro dose for 1y or post-surgery for 2y (whichever occurs last)
Adjuvant TX Informed Consent	X							
Review of Eligibility ^a	X							
Disease Status Assessment/Measurable disease	X ^e							X
Tumor Imaging		X ^e		X ^e	X ^e	X		X
Concomitant Medication Review	X	X	X	X	X	X	X	X
Trial Treatment Administration ^f		X	X	X	X			
Dispense vactosertib		X	X	X	X			
Post-study anticancer therapy status								X

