7.3.4 Definition of an Overdose Definition

For purposes of this trial, an overdose of pembrolizumab will be defined as any dose of 1,000 mg or greater. No specific information is available on the treatment of overdose of pembrolizumab. In the event of overdose, the patient should be observed closely for signs of toxicity. Appropriate supportive treatment should be provided if clinically indicated.

Vactosertib overdose is defined as any daily dose more than 900 mg or more than 1.5 times of weekly indicated dose. The effects of an overdose with vactosertib are unknown.

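### Section 3.4 gives 20 neoadjuvant vactosertib doses, but the schedule in the same sentence gives 10

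*Combined protocol and SAP*

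**What the plan says.** Section 3.4, which covers all participants, states one pembrolizumab dose and "20 doses of vactosertib (QD, 5 days per week for 2 weeks) prior to surgery". It gives no milligram amount per vactosertib dose.

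The neoadjuvant schedule appears in five other places:

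- Abstract, study drugs entry: "plus 200 mg vactosertib (PO QD, 5 days per week x 2 weeks".
- Section 1.3.2: "200 mg PO QD, 5 days per week for 2 weeks during the neoadjuvant treatment period".
- Section 5.1, Table 4: 200 mg once daily, 5 days per week, with treatment period "C1D1 through C1D14".
- Section 5.1.2: "Vactosertib will be administered once daily at 200 mg PO for 5 days followed by a 2-day resting period", for two weeks in the neoadjuvant phase.
- Section 6.2, Table 10, footnote j: "vactosertib will be taken QD, PO 5 days per week C1D1 through C1D14".

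Table 6 in section 5.2 also lists 200 mg once daily as the neoadjuvant starting level.

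Section 7.3.4 supplies the protocol's own yardstick for excess dosing: "Vactosertib overdose is defined as any daily dose more than 900 mg or more than 1.5 times of weekly indicated dose".

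**The concern.** The sentence in section 3.4 cannot be followed as written, because its count and its schedule describe different amounts of drug. It is current running text, not a damaged table or a remnant of an amendment log, and it is the only place where the protocol gives a number of neoadjuvant vactosertib doses.

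The figure of 20 is also not obviously a slip to someone reading section 3.4 alone. It is what twice-daily dosing would give over the same two weeks, and 200 mg twice daily is a regimen that this protocol uses, in adjuvant cycles 2 onward. What is at stake is a two-fold difference in the stated exposure to an investigational drug shortly before potentially curative liver surgery.

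**Working it through.** **Inputs**

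- Stated count: 20 doses (section 3.4).
- Stated schedule: 1 dose per day, 5 days per week, 2 weeks (section 3.4; the same in the abstract, 1.3.2, Table 4, 5.1.2 and Table 10 footnote j).
- Dose: 200 mg (all of those places except section 3.4 and footnote j). Applying it to the count in section 3.4 is an assumption.
- Overdose limits: more than 900 mg in a day, or more than 1.5 times the weekly indicated dose (section 7.3.4).

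**Step 1. Try to reproduce the stated count.** Doses = doses per day x days per week x weeks.

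| Reading | Calculation | Doses |
|---|---|---|
| Schedule as written | 1 x 5 x 2 | 10 |
| Once daily, no rest days, 2 weeks | 1 x 7 x 2 | 14 |
| Twice daily, 5 days per week, 2 weeks | 2 x 5 x 2 | 20 |
| Once daily, 5 days per week, 4 weeks | 1 x 5 x 4 | 20 |

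The schedule as written does not give 20; the ratio is 20 / 10 = 2.0. Of the readings tried, only the last two give 20. The first of these contradicts the once-daily frequency and the second contradicts the two-week period.

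**Step 2. Convert to exposure at 200 mg per dose.** 10 x 200 mg = 2,000 mg; 20 x 200 mg = 4,000 mg.

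**Step 3. Compare with the weekly overdose limit, taking the once-daily schedule as the indicated one.**

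- Weekly indicated dose: 200 mg x 5 = 1,000 mg.
- Limit: 1.5 x 1,000 mg = 1,500 mg, which is 1,500 / 200 = 7.5 doses in a week.
- If 20 doses are taken within two weeks, with *a* in one week and 20 - *a* in the other, the larger week holds at least 10 doses, or at least 10 x 200 mg = 2,000 mg.
- Ratio: 2,000 / 1,000 = 2.0, above 1.5 however the doses are split.

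**Step 4. Compare with the daily limit.** Twenty doses spread evenly over 10 dosing days are 2 per day: 2 x 200 mg = 400 mg, below 900 mg. This limb is not met.

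**Step 5. See what step 3 depends on.**

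- If 20 doses in two weeks were itself the indicated regimen, the weekly indicated dose would be 2,000 mg and the ratio 2,000 / 2,000 = 1.0, so no limit would be exceeded.
- If the 20 doses were taken once daily over four weeks, each week would hold 1,000 mg, again a ratio of 1.0.

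**The case against.** The strongest case on the other side is that this is an isolated miscount in a summary section. The schedule stands beside the number in the same sentence, and every other statement of the neoadjuvant regimen agrees with that schedule. Section 5.1 directs staff to the flow charts and to Tables 4 and 5 for administration. To give 20 doses in two weeks, staff would have to override all of these. This stands as an argument about likelihood: actual misdosing is improbable. It does not remove the contradiction from a sentence that covers every participant.

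Three stronger readings are tempting, and the documents do not support them.

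- A reader might infer that the protocol prescribes an overdose. It does not. A patient on the once-daily schedule takes 10 doses and exceeds nothing. The weekly limit is exceeded only if that schedule is the indicated one and someone acts on the count within the two weeks.
- A reader might infer that the count distorts compliance or the definition of a completed course. The protocol defines no vactosertib compliance percentage and no completion rule by dose count. Section 6.1.4 lets surgery proceed when vactosertib cannot be completed, unless there are concerns about the safety of the surgery. Nor would a fixed count be a sound denominator. Table 10 allows surgery 7 to 14 days after the first dose, so a patient operated on at 7 days could take only about 1 x 5 x 1 = 5 doses on the stated schedule without any departure from the protocol.
- A reader might infer that the primary analysis changes. Section 8.4.1 takes patients with evaluable paired specimens for the primary outcome, and those with at least one dose of either drug (plus a laboratory or vital sign measurement) for the treated population. Neither set depends on the number of vactosertib doses.

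**Conclusion.** The contradiction is real and exact: section 3.4 states 20 doses and a schedule that yields 10. No assumption is needed for that. The exposure figures of 2,000 mg and 4,000 mg assume 200 mg per dose, which section 3.4 does not state but the other sections do.

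The safety consequence is conditional. It needs the once-daily schedule as the indicated regimen (1,000 mg per week) and all 20 doses of 200 mg taken within the two weeks. At least one week would then reach at least 2.0 times the weekly indicated dose, against a limit of 1.5, while the 900 mg daily limit would not be reached.

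The point deserves correction because the wrong figure concerns pre-surgical exposure to an investigational drug. The agreement among the other sections keeps the practical risk low.

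**What to change.** Reconcile section 3.4 with the abstract, section 1.3.2, Table 4, section 5.1.2 and footnote j of Table 10, so that one neoadjuvant dose count and one schedule appear throughout. The sponsor must settle which is intended; this review does not choose between them.

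If the schedule repeated in the other sections is confirmed, the cost is one number in an amendment. If the count were confirmed instead, each of those sections would have to change, and the weekly indicated dose behind the overdose definition in section 7.3.4 would need to be restated. No change to the analysis populations or to the primary analysis follows from this point.
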